6.1. Adverse Events Assessment

The Investigators will monitor each patient for clinical and laboratory evidence of adverse events on a routine basis throughout the study. The Investigator will assess and record any adverse event in detail including the date of onset, event diagnosis (if known) or sign/symptom, severity, time course, duration and outcome, relationship of the adverse event to study drug, and any action(s) taken. For serious adverse events not considered "probably related" to study drug, the Investigator will provide an "Other" cause of the event. For adverse events to be considered intermittent, the events must be of similar nature and severity. Adverse events, whether in response to a query, observed by site personnel, or reported spontaneously by the patient will be recorded. All adverse events will be followed to a satisfactory conclusion.

6.2. Study Monitoring

6.2.1. Data Safety Monitoring Committee at Georgetown

The Georgetown Lombardi Comprehensive Cancer Center (LCCC) will be responsible for the data and safety monitoring of this trial. As this study is an Investigator initiated Phase II study utilizing investigational agents and FDA-approved off label therapies, it is considered a high risk study which requires real-time monitoring by the PI and study team and quarterly reviews by the LCCC Data and Safety Monitoring Committee (DSMC).

The Principal Investigator, [name], and the Study Chairs will review the data including safety monitoring at their monthly teleconferences with participating sites.

SAEs are required to be reported to the local and to the Georgetown IRB according to the IRB reporting guidelines. Based on SAEs, the IRB retains the authority to suspend further accrual pending more detailed reporting and/or modifications to further reduce risk and maximize the safety of participating patients.

Progress on the trial and the toxicities experienced will be reviewed by the LCCC Data and Safety Monitoring Committee every 3 months from the time the first patient is enrolled on the study. Results of the DSMC meetings will be forwarded to the IRB with recommendations regarding need for study closure.

DSMC recommendations should be based not only on results for the trial being monitored as well as on data available to the DSMC from other studies. It is the responsibility of the PI to ensure that the DSMC is kept

apprised of non-confidential results from related studies that become available. It is the responsibility of the DSMC to determine the extent to which this information is relevant to its decisions related to the specific trial being monitored.

A written copy of the DSMC recommendations will be given to the trial PI and the IRB. If the DSMC recommends a study change for patient safety or efficacy reasons the trial PI must act to implement the change as expeditiously as possible. In the unlikely event that the trial PI does not concur with the DSMC recommendations, then the LCCC Associate Director of Clinical Research must be informed of the reason for the disagreement. The trial PI, DSMC Chair, and the LCCC Associate Director for Clinical Research will be responsible for reaching a mutually acceptable decision about the study and providing details of that decision to the IRB. Confidentiality must be preserved during these discussions. However, in some cases, relevant data may be shared with other selected trial Investigators and staff to seek advice to assist in reaching a mutually acceptable decision.

If a recommendation is made to change a trial for reasons other than patient safety or efficacy the DSMC will provide an adequate rationale for its decision. If the DSMC recommends that the trial be closed for any reason, the recommendation will be reviewed by the Associate Director for Clinical Research at LCCC. Authority to close a trial for safety reasons lies with the IRB, with the above described input from DSMC and the Associate Director for Clinical Research.

Of note, the DSMC will also review the safety data of the patients enrolled outside of Georgetown University. The Georgetown Multicenter Project Manager(s) will be tasked with requesting primary source documentation for patients enrolled outside of Georgetown University, as needed. In addition, the data managers at each site will be entering data into the Georgetown database, so that all data will be available for the DSMC at Georgetown to review. Records should be sent via email to the Georgetown Multicenter Project Manager(s) and [name].

6.3. Adverse Event and Toxicity Definitions

6.3.1. Adverse Events

An AE is defined as any untoward medical occurrence in a patient or clinical investigation patient administered a pharmaceutical product and which does not necessarily have a causal relationship with this treatment. An adverse event can therefore be any unfavorable and unintended sign (including an abnormal laboratory finding), symptom, or disease temporally associated with the use of a medicinal (investigational) product, whether or not the event is considered causally related to the use of the product. Such an event can result from use of the drug as stipulated in the protocol or labeling, as well as from accidental or intentional overdose, drug abuse, or drug withdrawal. Any worsening of a pre-existing condition or illness is considered an adverse event. Laboratory abnormalities and changes in vital signs are considered to be adverse events only if they result in discontinuation from the study, necessitate therapeutic medical intervention, and/or if the Investigator considers them to be adverse events.

An elective surgery/procedure scheduled to occur during a study will not be considered an adverse event if the surgery/procedure is being performed for a pre-existing condition and the surgery/procedure has been pre-planned prior to study entry. However, if the pre-existing condition deteriorates unexpectedly during the study (e.g., surgery performed earlier than planned), then the deterioration of the condition for which the elective surgery/procedure is being done will be considered an adverse event.

All AEs experienced by a patient, irrespective of the suspected causality, will be monitored until the AE has resolved, any abnormal laboratory values have returned to baseline or stabilized at a level acceptable to the Investigator, until there is a satisfactory explanation for the changes observed, until the patient is lost to follow-up, or until the patient has died.

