3.5.2.3. Hematopoietic growth factors

Hematopoietic growth factors are not permitted during study treatment. The patient should be referred to a hematologist for further evaluation (1) if frequent transfusions are required or (2) if the treatment-related hematologic toxicities have not recovered to CTCAE Grade 1 or less after 4 weeks.

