4.3.8. Laboratory samples

Laboratory samples for this study will be assessed using the certified laboratory at the Investigators' institutions or at a clinical laboratory such as Quest or LabCorp and these data will be used for all data analysis. The Principal Investigator or sub-Investigator will review, initial and date all laboratory results. Any laboratory value outside the reference range that is considered clinically significant by the Investigator will be followed as appropriate. Clinically significant laboratory values will be recorded as adverse events if they meet the criteria as specified in Section 6.3.

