Grade 1 and 2	No requirement for dose interruption or dose reduction
Anemia Grade \geq 3 (hemoglobin < 8 g/dL or transfusion indicated)	
1st occurrence: Hold SM-88 and MPS; monitor at least weekly and if hemoglobin recovers to ≥ 8 g/dL within 28 days then resume drugs and decrease SM-88 to dose level -1. Transfusion of blood and blood products are permitted.Recurrence: Hold SM-88 and MPS; monitor at least weekly and if hemoglobin recovers to ≥ 8 g/dL within 28 days resume drugs and patient can remain on study at investigator discretion.Permanently discontinue SM-88 and MPS if these parameters have not been met after 28 days of dose interruption.
Neutropenia Grade \geq 3 (ANC $< 1000/\text{mm}^3$) associated with a documented infection or fever $\geq 38.5^\circ\text{C}$	
1st occurrence: Hold SM-88 and MPS; monitor at least weekly and if ANC recovers ($\text{ANC} \geq 1000/\text{mm}^3$) within 28 days, then resume drugs and decrease SM-88 to dose level-1. Hematopoietic growth factors are not permitted.Recurrence: Hold SM-88 and MPS; monitor at least weekly and if ANC recovers ($\text{ANC} \geq 1000/\text{mm}^3$) within 28 days then resume drugs at same dose level.Permanently discontinue SM-88 and MPS if these parameters have not been met after 28 days of dose interruption.
Grade 4 neutropenia (ANC $< 500/\text{mm}^3$)	
1st occurrence: Hold SM-88 and MPS. Monitor at least weekly and if ANC recovers to $\geq 1000/\text{mm}^3$ in ≤ 7 days, then resume study drugs at same dose level. If ANC remains $< 1000/\text{mm}^3$ for > 7 days, hold SM-88 and MPS until ANC $\geq 1000/\text{mm}^3$ and decrease SM-88 to dose level -1.Recurrence: Hold SM-88 and MPS; monitor at least weekly and if ANC recovers ($\text{ANC} \geq 1000/\text{mm}^3$) within 28 days then decrease SM-88 to dose level -1 or resume drugs at same dose level if already at dose level -1.Permanently discontinue SM-88 and MPS if these parameters have not been met after 28 days of dose interruption.

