8.4.2.4. Safety Assessments

Overall safety monitoring will be performed throughout the study. The safety of the SM-88 therapy will be assessed by evaluating study drug exposure, adverse events, serious adverse events, and all deaths.

A summarization of the number of days and/or cycles patients were exposed to study drug will be provided. Adverse events (and serious adverse events) will be graded and recorded throughout the study and during the follow-up period according to NCI CTCAE Version 5.0. Toxicities will be characterized in terms of seriousness, causality, toxicity grading, and action taken with regard to trial treatment. The percentage of patients experiencing an adverse event at a given severity, NCI CTCAE toxicity grade, and relationship to study drug will be provided. The number of patient deaths throughout the study will be summarized.

8.4.3. Exploratory Endpoints:

Descriptive statistics will be used to analyze any changes in cell-free DNA (cfDNA) measurement at baseline (pre-treatment on C1D1), during the SM-88 therapy, and at disease progression time points.

Baseline Characteristics

All baseline summary statistics and analyses will be based on characteristics prior to the initiation of study drug. Frequency and percentages for categorical variables, and mean (SD) or median (IQR, interquartile range) for the continuous variables based on the normalization of the data.

9. Correlative Research Management

9.1. cfDNA

Blood sample collection for analysis of cfDNA analysis will be collected at multiple time points: baseline (pre-treatment), C2D1, C3D1, at each additional restaging scan (every 8-12 weeks) and disease progression. cfDNA samples will be banked at Georgetown University, and eventually shipped to Foundation Medicine for analysis.

All specimens will be collected in two (2) 10 mL Streck cell-free DNA collection tubes (DNA BCT catalog # 230470). These vials shall be processed as per the laboratory instructions provided by Foundation Medicine, and categorized and banked at Georgetown as per protocol. Refer to the Lab Manual for more details on collection, processing, and storage instructions.

10. Ethical Considerations

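### Cytopenias that force a Table 5 treatment hold count as adverse events only at the investigator's discretion, so the AE percentages can under-count them

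*Combined protocol and SAP*

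**What the plan says.** **AE definition (Section 6.3.1).** The section opens broadly: an AE can be "any unfavorable and unintended sign (including an abnormal laboratory finding"), whatever its cause. The same paragraph then narrows this for laboratory values: "Laboratory abnormalities and changes in vital signs are considered to be adverse events only if they result in discontinuation from the study", or if they "necessitate therapeutic medical intervention, and/or if the Investigator considers them to be adverse events". That makes three routes: study discontinuation, therapeutic intervention and investigator opinion.

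**Laboratory section (4.3.8).** It adds no route of its own: "Clinically significant laboratory values will be recorded as adverse events if they meet the criteria as specified in Section 6.3".

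**Dose modification (Section 5.6, Table 5).** Several hematology rows act on the laboratory value alone. The Grade 4 neutropenia row, for example, begins "1st occurrence: Hold SM-88 and MPS. Monitor at least weekly and if ANC recovers to" the threshold. Rows for thrombocytopenia and anemia also require holds, and some rows add an SM-88 reduction. Section 3.5.2.3 states: "Hematopoietic growth factors are not permitted during study treatment".

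**Toxicity management (Section 6.8.1).** The general rules for delay and discontinuation are introduced as applying when a patient has an AE, and they point to Table 5. For a hematologic interruption, weekly counts continue until what the section calls the AE has resolved or the patient leaves the study.

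**Safety analysis (Section 8.4.2.4).** "The percentage of patients experiencing an adverse event at a given severity, NCI CTCAE toxicity grade, and relationship to study drug will be provided". No separate summary of graded laboratory values is planned.

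**The concern.** The AE definition and the dose-modification table use different triggers. Table 5 treats a Grade 3-4 cytopenia as serious enough to stop all four drugs. Section 6.3.1 does not treat that stop as a reason to record an AE. Such an event can be handled exactly as the plan requires and still be absent from the AE listing.

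Safety and tolerability is a secondary objective (Sections 2.2 and 8.1.2), and its graded results are built from recorded AEs. Relatedness and the attribution among SM-88, methoxsalen, phenytoin and sirolimus (Section 6.3.4) are also assigned to AEs. A cytopenia that is not recorded as an AE therefore gets neither a grade nor a causality entry in the reported results. Five sites would apply a rule that rests on opinion, so the reported rate would partly reflect recording habits.

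**Working it through.** The plan states no figure on this point, so there is none to reproduce. The check compares the texts and then bounds the possible size.

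**Step 1. Run Table 5 events through the three routes of Section 6.3.1.** Each event is a first occurrence that recovers in time for treatment to resume.

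| Event | Table 5 action | Study discontinuation? | Therapeutic intervention? | Route left |
|---|---|---|---|---|
| Grade 4 neutropenia, afebrile, recovered in 7 days or less | Hold, resume same level | No | None required; growth factors barred | Opinion |
| The same, recovery after more than 7 days | Hold, SM-88 to level -1 | No | None required; growth factors barred | Opinion |
| Grade 3 thrombocytopenia, no bleeding | Hold, resume same level | No | None required | Opinion |
| Grade 4 thrombocytopenia, no bleeding | Hold, SM-88 to level -1 | No | None required | Opinion |
| Hemoglobin below 8 g/dL, not transfused | Hold, SM-88 to level -1 | No | None given | Opinion |

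In every row the two objective routes fail and only investigator opinion remains.

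**Step 2. Find the limits of the gap.** Transfused anemia, and cytopenia with treated infection or bleeding, meet the intervention route. Events that end in discontinuation from the study meet the first route. For non-hematologic toxicity of Grade 3 or higher, Table 5 exempts laboratory values with no clinical correlate from the hold, so a chemistry value alone should seldom force one. The gap is essentially hematologic.

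**Step 3. See what is captured elsewhere.** Section 5.6 puts all dose modifications in the chart and CRF, and Section 6.8.1 requires interruptions to be recorded with their reasons. The synopsis and the secondary objectives count dose delays and reductions, although the list in Section 8.4.2.4 covers only exposure, AEs, SAEs and deaths. The hold is therefore not lost. What can be lost is the event's grade and causality in the AE results.

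**Step 4. Bound the size.** Inputs: N = 50 (Section 3.1.2, used as a round denominator); a true rate T of hold-forcing Grade 3-4 cytopenia, which is assumed because the documents give none; and the share c recorded as AEs, also assumed.

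Reported % = T x c; expected patients = 50 x T.

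| T | Expected patients | Reported, c = 0 | Reported, c = 0.5 | Reported, c = 1 |
|---|---|---|---|---|
| 2% | 1 | 0% | 1% | 2% |
| 5% | 2.5 | 0% | 2.5% | 5% |
| 10% | 5 | 0% | 5% | 10% |
| 20% | 10 | 0% | 10% | 20% |

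A confidence interval around the reported count would not cover this, because it describes sampling error and not under-recording.

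**The case against.** The strongest reply is that the protocol already treats these events as AEs. Section 6.8.1 does so in its wording, and the opening of the definition in 6.3.1 includes abnormal laboratory findings. Section 6.1 has investigators look for laboratory evidence of AEs, and Section 6.3.2 gives blood dyscrasias as an example of an important medical event. Section 8.4.2.4 describes toxicities by the action taken on trial treatment, which presupposes that events causing a hold are in the data. An investigator who stops four drugs for a neutrophil count will usually call it an AE. Much of this stands. It shows the likely intent and makes the 0% end of the range improbable. It does not remove the restrictive sentence, and the SAE criteria apply only to events already classed as AEs. The two texts need reconciling.

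It could also be said that a hold is itself a therapeutic medical intervention. That reading would close the gap, but the documents never adopt it.

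Prior experience is a fair point on size. Section 1.3 reports no dose-limiting toxicities, and none of the Grade 3 or higher events it names is a cytopenia. Against that, Section 6.8.3.1 lists thrombocytopenia, granulocytopenia and pancytopenia among reported complications of phenytoin, so such events are foreseeable here.

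A reader might infer that the monitoring committee's review has the same blind spot. The documents do not support this: Section 6.2.1 has the committee review the toxicities experienced and makes all entered site data available to it.

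**Conclusion.** The point holds as a conflict between Section 6.3.1 on one side and Table 5 and Section 6.8.1 on the other. An uncomplicated Grade 3-4 cytopenia that interrupts treatment enters the AE percentages and the attribution only by individual choice. The under-count cannot be sized from the documents. It lies between nothing and the whole true rate, and the rates of 2% to 20% used above are assumptions.

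A reader might infer that all Grade 3-4 laboratory toxicities are exposed, or that the plan tells sites to leave these events out. Neither follows. The exposure is mainly hematologic, and the investigator may always record the event. Nor does the conflict call for a rule making every laboratory or vital-sign change of Grade 3 or higher an AE. That would go beyond the conflict and override judgement where the plan deliberately leaves it. The primary endpoint and the two-stage decision rule are unaffected.

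**What to change.** 1. In Section 6.3.1, add that a laboratory abnormality leading to a hold, delay or reduction of any study drug is recorded as an AE. This brings the definition into line with Section 6.8.1.
2. In Section 8.4.2.4, add a table of worst post-baseline CTCAE grade, as a shift from baseline, from the CBC and chemistry values already collected under the study calendar. It gives a laboratory toxicity rate that does not depend on AE recording.

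The cost is one clause, one table from existing data and a few more AE entries. Reported AE rates may look slightly less favourable. No dose rule, visit, sample or sample size changes.

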6.3.2. Serious Adverse Events

If an adverse event meets any of the following criteria, it is to be reported to the DSMC as a SAE per DSMC reporting guidelines.

- 1) **Death of Patient** An event that results in the death of a patient.
- 2) **Life-Threatening** An event that, in the opinion of the Investigator, would have resulted in immediate fatality if medical intervention had not been taken. This does not include an event that would have been fatal if it had occurred in a more severe form.
- 3) **Hospitalization** (unless planned for observation, protocol compliance, elective procedures, social reasons) or
- 4) **Prolongation of Hospitalization** An event that results in an admission to the hospital for any length of time or prolongs the patient's hospital stay. This does not include an emergency room visit or admission to an outpatient facility.
- 5) **Congenital Anomaly** An anomaly detected at or after birth, or any anomaly that results in fetal loss.
- 6) **Persistent or Significant Disability/Incapacity** An event that results in a condition that substantially interferes with the activities of daily living of a study patient. Disability is not intended to include experiences of relatively minor medical significance such as headache, nausea, vomiting, diarrhea, influenza, and accidental trauma (e.g., sprained ankle).
- 7) **Important Medical Event Requiring Medical or Surgical Intervention to Prevent Serious Outcome** An important medical event that may not be immediately life-threatening or result in death or hospitalization, but based on medical judgment may jeopardize the patient and may require medical or surgical intervention to prevent any of the outcomes listed above (i.e., death of patient, life-threatening, hospitalization, prolongation of hospitalization, congenital anomaly, or persistent or significant disability/incapacity). Examples of such events include allergic bronchospasm requiring intensive treatment in an emergency room or at home, blood dyscrasias or convulsions that do not result in inpatient hospitalization, or the development of drug dependency or drug abuse.
- 8) **Spontaneous Abortion** Miscarriage experienced by study patient.

Disease progression is an efficacy criterion and is therefore not considered an AE or SAE (even if fatal). Disease progression should be documented. If AEs/SAEs occur in relation to disease progression that are not consistent with the natural progression of the patient's disease, these AEs/SAEs must be reported per AE/SAE reporting requirements.

6.3.3. Adverse Event Severity

The study Investigator will rate the severity of each adverse event according to the NCI CTCAE Version 5.0. For adverse events not captured by the NCI CTCAE Version 5.0, the following should be used:

- 1) **Grade 1 (Mild)** The adverse event is transient and easily tolerated by the patient.
- 2) **Grade 2 (Moderate)** The adverse event causes the patient discomfort and interrupts the patient's usual activities.
- 3) **Grade 3/4 (Severe or Life Threatening)** The adverse event causes considerable interference with the patient's usual activities and may be incapacitating or life-threatening.
- 4) **Grade 5 (Severe, Resulting in Death)** The adverse event resulted in death of the patient.

6.3.4. Relationship to Study Drug

6.3.4.1. Assessment of Toxicity Relatedness to Study Medications

The Investigator will use the following definitions to assess the relationship of the adverse event to the use of study drug(s).

- 1) **Definitely Related** An adverse event has a clear temporal relationship to study drug(s) and/or recurs on re-challenge and another cause of event is extremely unlikely.
- 2) **Probably Related** An adverse event has a strong temporal relationship to study drug(s) or recurs on re-challenge and another cause of event is unlikely or significantly less likely.
- 3) **Possibly Related** An adverse event has a strong temporal relationship to the study drug(s) and another cause of event is equally or less likely compared to the potential relationship to study drug.
- 4) **Probably Not Related** An adverse event has little or no temporal relationship to the study drug(s) and/or a more likely Other cause of event exists.

5) **Not Related** An adverse event is due to an underlying or concurrent illness or effect of another drug(s) and is not related to the study drug (e.g., has no temporal relationship to study drug or has a much more likely Other cause of event).

